4.0 Test Schedule

Cycle = 28 days

Tests and procedures	Active Monitoring Phase						
	≤14 days prior to registration	Cycle 1 Day 1 (± 2 days) prior to treatment	Cycle 1 Days 8, 15, 22 prior to treatment	Cycle 2 and beyond Day 1 (± 2 days) prior to treatment	Q 8 weeks from Cycle 1 Day 1 (± 5 days)	Every 3 Cycles starting at end of Cycle 3 (± 5 days)	End of treatment
History and exam, wt, ECOG	X			X			X
Height, Child Pugh score	X						
Vitals ³	X	X	X	X			X
Hematology group WBC, ANC, Hgb, PLT	X	X	X	X			X
Chemistry group Sodium, potassium, chloride, bicarbonate, total protein, albumin, calcium, glucose, BUN, total bilirubin, creatinine, alkaline phosphatase, SGOT (AST), SGPT (ALT)	X	X		X			X
Amylase ^R	X	X	X	X			
Lipase ^R	X	X	X	X			
CA19-9		X		X ⁵			
EKG ^R	X					X	
Echocardiogram	X			X ¹⁰			
Tumor measurement and Imaging (CT or MRI as clinically)	X ¹				X ²		

indicated)							
Pregnancy test	X ⁴						
Patient questionnaire booklet	X ⁹			X ⁹			
Adverse event assessment	X		X	X			
Research Archival Tissue (optional)	X ⁸						
Research Tissue Biopsy (optional)				X ^{7,R}			X ⁶
Research blood samples (Optional)	X			X			X

1. Imaging studies such as CT scans, and MRIs can be performed ≤ 28 days prior to registration. Use same imaging throughout the study. Assessment by physical exam should be done ≤ 14 days prior to registration.
 2. Tumor assessment must be performed at least every 8 weeks. Tumor assessment should be performed at any time during the treatment cycle that disease progression is clinically suspected so that patient can go off treatment and receive other therapy.
 3. Includes weight, blood pressure, pulse and temperature
 4. Women of childbearing potential only. Must be done ≤ 7 days prior to registration.
 5. Only to be collected if $> \text{ULN}$ on Cycle 1 Day 1
 6. If patient has experienced disease progression and at such time a standard of care biopsy is ordered by the treating physician, waste specimen will be collected, fresh frozen and stored for future correlative studies. Perform only if archival specimen was available.
 7. Perform only if archival specimen was available.
 8. Archival FFPE and/or fresh frozen tissue collected in setting of standard of care procedures.
 9. Patient questionnaire booklet must be used; copies are not acceptable for this submission. Booklet should be completed by patient prior to review of treatment response and discussions of patient's general health since last treatment evaluation.
 - 10 Echocardiograms to be completed at baseline and then every 2 cycles for the duration of study treatment.
- R Research funded (see Section 19.0).

5.0 Stratification Factors: None.

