8.1 Dose Levels (Based on Adverse Events in Tables 8.2)

Dose Level	Ponatinib
0*	45mg PO once daily
-1	30mg PO once daily
-2	15mg PO once daily

*Dose level 0 refers to the starting dose.

8.2

→ → *Use the NCI Common Terminology Criteria for Adverse Events (CTCAE) version 4.0* unless otherwise specified* ← ←

CTCAE System/Organ/Class (SOC)	ADVERSE EVENT	AGENT	ACTION**
BASED ON INTERVAL ADVERSE EVENT			
Investigations	Neutrophil count decreased ≥ Grade 3	Ponatinib	Omit ponatinib Resume at 45 mg after recovery to ≤ grade 1 Recurrence at 45 mg: Omit ponatinib Resume at 30 mg after recovery to ≤ grade 1 Recurrence at 30 mg: Omit ponatinib Resume at 15 mg after recovery to ≤ grade 1 Recurrence at 15 mg: Discontinue ponatinib

→ → Use the NCI Common Terminology Criteria for Adverse Events (CTCAE) version 4.0* unless otherwise specified ← ←			
CTCAE System/Organ/Class (SOC)	ADVERSE EVENT	AGENT	ACTION**
	Platelet count decreased \geq Grade 3		
Omit ponatinib Resume at 45 mg after recovery to \leq grade 1
 
Recurrence at 45 mg: Omit ponatinib Resume at 30 mg after recovery to \leq grade 1
 
Recurrence at 30 mg: Omit ponatinib Resume at 15 mg after recovery to \leq grade 1
 
Recurrence at 15 mg: Discontinue ponatinib

	Serum amylase increased \geq Grade 3 with no radiographic findings	Ponatinib	
Omit ponatinib Resume at 45 mg after recovery to \leq grade 1
 
Recurrence at 45 mg: Omit ponatinib Resume at 30 mg after recovery to \leq grade 1
 
Recurrence at 30 mg: Omit ponatinib Resume at 15 mg after recovery to \leq grade 1
 
Recurrence at 15 mg: Discontinue ponatinib

	Serum amylase increased \geq Grade 3 with radiographic findings or Grade 4	Ponatinib	
Omit ponatinib Repeat imaging according to clinical care After resolution by imaging, resume at 30 mg after recovery to \leq grade 1
 
Recurrence at 30 mg: Repeat above Resume at 15 mg after recovery to \leq grade 1
 
Recurrence at 15 mg: Discontinue ponatinib

→ → Use the NCI Common Terminology Criteria for Adverse Events (CTCAE) version 4.0* unless otherwise specified ← ←			
CTCAE System/Organ/Class (SOC)	ADVERSE EVENT	AGENT	ACTION**
	Alanine aminotransferase increased (ALT) and/or Aspartate aminotransferase increased (AST) ≥ Grade 3	Ponatinib	Omit ponatinib Resume at 30 mg after recovery to ≤ grade 1 Recurrence at 30 mg: Omit ponatinib Resume at 15 mg after recovery to ≤ grade 1 Recurrence at 15 mg: Discontinue ponatinib

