Other Non-Hematologic events	≥ Grade 3	Ponatinib	Omit drug and follow patient at least weekly until adverse event has resolved to grade ≤ 2, restart agent at next lower dose level. See sections 8.41 through 8.47 for guidance on other non-hematologic events

* Located at http://ctep.cancer.gov/protocolDevelopment/electronic_applications.ctc.htm

** Use the following to describe actions in the Action column:

- Omit = Treatment is not given for the day/days that are omitted and will not be made up, but treatment may resume once the adverse event has resolved as mandated in Table 8.2. For example, if treatment is omitted on Day 8, but the adverse event has resolved by Day 15, treatment may resume on Day 15.
- Hold/Delay = Treatment can be made up as part of this cycle
- Discontinue = Treatment is totally stopped

NOTE: If the patient experiences a significant adverse event requiring a dose reduction at the start of the next cycle, then the dose will remain lowered for that entire subsequent cycle. If that cycle is completed with no further adverse events >Grade 2, then the dose may be increased, at the investigator's discretion, one level at a time, in the following cycles.

NOTE: Adverse events requiring a dose-reduction step for any or all drugs beyond the two dose-reduction steps (levels -1 and -2) will be at the discretion of the treating physician, if the decision is made for the patient to be kept on study. These dose reductions must be clearly recorded in reported clinical data.

- 8.3 A new course of treatment may begin on the scheduled Day 1 of a new cycle if:
- The ANC is $\geq 1500/\mu\text{L}$;
 - The platelet count is $\geq 75,000/\mu\text{L}$;
 - Any other Ponatinib related adverse event that may have occurred has resolved to \leq Grade 1 or baseline severity.

If these conditions are not met on scheduled Day 1 of a new cycle, the subject will be evaluated at least weekly and the new cycle of treatment will not be initiated until the adverse event has resolved as described above.

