When therapy is resumed it will be considered day one of this new cycle. If Ponatinib was halted during the previous cycle and was restarted with a one-level dose reduction without requiring an interruption for the remainder of the cycle, then that reduced dose level will be initiated on Day 1 of the new cycle. **If ponatinib was omitted for the remainder of the previous cycle or if the new cycle is delayed due to adverse event newly encountered on the scheduled Day 1**, then the scheduled cycle will be started with a one-level dose reduction. If the study drug cannot be restarted within 28 days of the

scheduled Day 1 of a given cycle, the patient will be removed from study treatment and will proceed to event monitoring.

8.4 Additional adverse event guidance:

8.41 Hepatotoxicity: Iclusig can cause hepatotoxicity, including liver failure and death. Fulminant hepatic failure leading to death occurred in an Iclusig-treated patient within one week of starting Iclusig. Two additional fatal cases of acute liver failure also occurred. The fatal cases occurred in patients with blast phase CML (BP-CML) or Philadelphia chromosome positive acute lymphoblastic leukemia (Ph+ ALL). Severe hepatotoxicity occurred in all disease cohorts. Iclusig treatment may result in elevation in ALT, AST, or both. Monitor liver function tests at baseline, then at least monthly or as clinically indicated. Interrupt, reduce, or discontinue Iclusig as clinically indicated.

8.42 Pancreatitis: Clinical pancreatitis occurred in 6% (28/449) of patients (5%, grade 3) treated with Iclusig. Pancreatitis resulted in discontinuation or treatment interruption in 6% of patients (25/449). The incidence of treatment-emergent lipase elevation was 41%. Check serum lipase every 2 weeks for the first 2 months and then monthly thereafter or as clinically indicated. Consider additional serum lipase monitoring in patients with a history of pancreatitis or alcohol abuse. Dose interruption or reduction may be required. In cases where lipase elevations are accompanied by abdominal symptoms, interrupt treatment with Iclusig and evaluate patients for pancreatitis. Do not consider restarting Iclusig until patients have complete resolution of symptoms and lipase levels are less than 1.5 x ULN.

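### Patient safety, low-cost improvement: no liver test is scheduled from the pre-dose Cycle 1 Day 1 sample to Cycle 2 Day 1, although blood is already drawn on Days 8, 15 and 22

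*Combined protocol and SAP*

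**What the plan says.** The Section 4.0 grid lists alkaline phosphatase, AST and ALT ("alkaline phosphatase, SGOT (AST), SGPT (ALT") and total bilirubin once only, in the 14-analyte chemistry group. That row is marked at screening, at "Cycle 1 Day 1 (± 2 days) prior to treatment", on Day 1 of Cycle 2 and later cycles, and at end of treatment. Its cell under "Cycle 1 Days 8, 15, 22 prior to treatment" is empty. The hematology, amylase and lipase rows are marked there, as are vital signs and adverse event assessment.

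Section 8.41 sets the liver frequency: "Monitor liver function tests at baseline, then at least monthly or as clinically indicated". It reports three fatal cases of liver failure, one of them within the first week of dosing, and adds: "Severe hepatotoxicity occurred in all disease cohorts". Section 8.42 sets a different frequency for the pancreas: "Check serum lipase every 2 weeks for the first 2 months and then monthly thereafter or as clinically indicated".

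Table 8.2 has two hepatic rows. The first, "Alanine aminotransferase increased (ALT) and/or Aspartate aminotransferase increased (AST") at Grade 3 or higher, requires omission and then resumption at 30 mg after recovery to Grade 1 or lower. The second adds bilirubin of at least 2 x ULN and alkaline phosphatase above 2 x ULN, and requires permanent discontinuation.

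**The concern.** Table 8.2 is meant to act within a cycle. It is headed as based on interval adverse events, and the footnote defining an omitted dose uses Days 8 and 15 as its example. Its other laboratory rows (neutrophils, platelets, amylase) each have a scheduled test on Days 8, 15 and 22. Only the two hepatic rows do not.

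At stake is the patient whose transaminases reach Grade 3 or higher in Cycle 1 without symptoms. No scheduled test would show it before Cycle 2 Day 1. Unless something else interrupts dosing, the patient would stay on 45 mg daily while the protocol's own rule says to omit the drug. The protocol describes this toxicity as potentially fatal.

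**Working it through.** The plan states no figure for this gap, so there is none to reproduce. The check reads the grid and counts days.

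**Is the blank cell real?** The chemistry row has seven cells for seven column heads: screening X, Cycle 1 Day 1 X, Days 8/15/22 blank, Cycle 2+ Day 1 X, every 8 weeks blank, every 3 cycles blank, end of treatment X. The neighbouring rows line up in the same way, so the blank does not come from text extraction.

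**Inputs** (Section 4.0 unless noted)
- Cycle length: 28 days.
- Window: 2 days either side of Day 1 visits. None is printed for Days 8, 15 and 22, so these are taken as exact.
- Assumption: the first dose defines Day 1. The first sample must precede treatment, so it falls 0 to 2 days before that dose.
- Maximum accrual: 30 (Section 16.22). Stage 1: 10 evaluable patients (Section 16.211).

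**Gaps between scheduled liver tests.** Cycle 2 Day 1 falls 28 ± 2 = 26 to 30 days after the first dose.

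| Interval | Nominal | Range |
|---|---|---|
| Now: pre-dose sample to Cycle 2 Day 1 | 28 | 26 − 0 = 26 to 30 + 2 = 32 |
| With fix: pre-dose sample to Day 8 | 7 | 7 + 0 = 7 to 7 + 2 = 9 |
| With fix: Day 8 to 15, and Day 15 to 22 | 7 | 7 |
| With fix: Day 22 to Cycle 2 Day 1 | 7 | 7 − 2 = 5 to 7 + 2 = 9 |

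The longest gap falls from 28 to 7 days nominal, and from 32 to 9 at the extreme.

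**Doses at stake, one illustration.** Suppose a symptom-free Grade 3 rise is present on Day 8, a Day 8 result would be acted on the same day, and nothing else interrupts treatment. The current schedule then allows doses on Days 8 to 28: 28 − 8 + 1 = 21 doses of 45 mg that Table 8.2 would have omitted.

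**Does another scheduled check close the gap?** Section 8.3 ("A new course of treatment may begin on the scheduled Day 1 of a new cycle if") requires ponatinib-related events to have settled before a new cycle. It acts on Cycle 2 Day 1, where the gap ends.

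**Size of the addition.** 3 panels x 30 patients = 90 at most. If the trial stops after Stage 1, 3 x 10 = about 30.

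**The case against.** The strongest reply is that no rule is broken. Section 8.41 asks for liver tests at baseline and at least monthly, and the schedule delivers that. This stands. A reader might infer that Section 4.0 contradicts Section 8.41, or that weekly lipase testing shows the liver panel was left out by mistake. The documents support neither, because Sections 8.41 and 8.42 set different frequencies on purpose. The denser pancreatic testing shows only that the blood draws exist.

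Second, other safeguards narrow the exposed group:
- Adverse events are assessed on Days 8, 15 and 22, and clinically prompted liver tests are allowed.
- The nursing guidance in Section 15.195 says to monitor liver function, without an interval.
- The medication guide tells patients to seek help for jaundice, dark urine or sleepiness.
- Entry requires AST and ALT below 3 x ULN and bilirubin no higher than 1.5 x ULN.
- Anyone who stops in Cycle 1 has end-of-treatment chemistry.

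All of this stands, but none of it schedules a test for a symptom-free patient who keeps dosing.

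Third, the only dated liver event in the documents is the first-week death, and a Day 8 draw would have been too late for it. The fatal cases were in blast-phase CML or Ph+ ALL, not biliary cancer. Nothing in the documents places liver injury in Days 8 to 28, and the same monthly spacing recurs in later cycles. The case for Cycle 1 therefore rests on the severity of the hazard, the existing dose rule and the existing draws, not on a demonstrated rate.

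Fourth, more testing has a clinical cost. The ALT/AST row has no attribution condition, so in biliary cancer a disease-related or transient rise would also trigger omission and a step down to 30 mg. This stands as a trade-off. It is softened by the note under Table 8.2 that allows later re-escalation at the investigator's discretion.

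**Conclusion.** The point holds as an inexpensive safety improvement to a schedule that complies with its own minimum. For 28 nominal days after treatment starts, and up to 32, the two hepatic rows of Table 8.2 have no scheduled test behind them, while the other laboratory rows do. The day counts assume that the first dose is Day 1 and that the first sample is taken before it.

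The size of the benefit is not established. A reader might derive an expected number of affected patients from Section 15.17, which lists raised AST and ALT among effects seen in more than 10% of patients. That figure gives neither grade nor timing. It does not measure a Grade 3 or higher, symptom-free rise in Cycle 1, and no count should be built on it. The documents give neither a rate nor an onset time for that event.

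The change is worth making but does not affect the validity of the trial. The two-stage decision rule and the sample size are unchanged.

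**What to change.** In Section 4.0, add a hepatic panel row (AST, ALT, total bilirubin, alkaline phosphatase) marked at Cycle 1 Days 8, 15 and 22. Because these are 4 of 14 analytes in one grouped row, this needs a new row. The simpler alternative is to mark the existing chemistry cell and run the whole group.

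Give the addition the research-funded (R) marker and list it in Section 19.2. Amylase and lipase are on that list and chemistry is not, so without this step the tests could be charged to patients as routine care under Section 19.1.

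Cost: no extra visit or needle stick, and at most 90 panels (about 30 if the trial stops after 10 patients). The documents give no unit price, so the sponsor must make a funding decision. The team should also accept that some omissions or reductions may follow rises unrelated to ponatinib.

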- 10.14 Any serious adverse event occurring after the patient has provided informed consent, has started taking the study medication, and until 4 weeks after the patient has stopped study participation must be reported. This includes the period in which the study protocol interferes with the standard medical treatment given to a patient (e.g. treatment withdrawal during washout period, change in treatment to a fixed dose of concomitant medication). The period after discontinuing study drug may be extended if there is a strong suspicion that the drug has not yet been eliminated.

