10.4 Expedited Reporting Requirements for IND/IDE Agents

Expedited Reporting Requirements for Adverse Events that Occur on Studies under an IND/IDE within 30 Days of the Last Administration of the Investigational Agent/Intervention^{1,2}

FDA REPORTING REQUIREMENTS FOR SERIOUS ADVERSE EVENTS (21 CFR Part 312) NOTE: Investigators MUST immediately report to the sponsor ANY Serious Adverse Events, whether or not they are considered related to the investigational agent(s)/intervention (21 CFR 312.64) An adverse event is considered serious if it results in ANY of the following outcomes: 1) Death 2) A life-threatening adverse event 3) An adverse event that results in inpatient hospitalization or prolongation of existing hospitalization for ≥ 24 hours 4) A persistent or significant incapacity or substantial disruption of the ability to conduct normal life functions 5) A congenital anomaly/birth defect. 6) Important Medical Events (IME) that may not result in death, be life threatening, or require hospitalization may be considered serious when, based upon medical judgment, they may jeopardize the patient or subject and may require medical or surgical intervention to prevent one of the outcomes listed in this definition. (FDA, 21 CFR 312.32; ICH E2A and ICH E6).
		

ALL SERIOUS adverse events that meet the above criteria MUST be immediately reported to the sponsor within the timeframes detailed in the table below.
		
Hospitalization	Grade 2 Timeframes	Grade 3-5 Timeframes
Resulting in Hospitalization ≥ 24 hrs	7 Calendar Days (see below timelines)	24-Hour 3 Calendar Days
Not resulting in Hospitalization ≥ 24 hrs	Not required	

NOTE: Protocol specific exceptions to expedited reporting of serious adverse events are found in Section 10.41 of the protocol. Expedited AE reporting timelines are defined as:
 
 ○ “24-Hour; 3 Calendar Days” - The AE must initially be reported within 24 hours of learning of the AE, followed by a complete expedited report within 3 calendar days of the initial 24-hour report. ○ “7 Calendar Days” - A complete expedited report on the AE must be submitted within 7 calendar days of learning of the AE. Please report to ARIAD within 2 business days. 		

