10.41 Adverse Events of Special Interest (AESIs)

Vascular occlusive events have been identified as AESIs for ponatinib. These include arterial and venous thrombotic and occlusive adverse events that meet the criteria for SAEs (see section 10.1) and those adverse events that do not meet the SAE criteria. AESIs require ongoing monitoring by investigators and rapid identification and communication by the investigator to the study sponsor. All AESIs, whether SAEs or not, must be reported within 2 business days of the study sponsor awareness to ARIAD.

ARIAD has determined that the events listed below (whether considered serious or non-serious by investigators) should be considered AESIs:

- A. Myocardial infarction: The Third Universal Definition of Myocardial Infarction (Thygesen et al, 2012) is used to define MI
- B. Angina (newly diagnosed or worsening of existing angina or unstable angina)
- C. Coronary artery disease (CAD) (newly diagnosed or worsening of existing CAD) or symptoms that may reflect cardiovascular disease (Thygesen et al, 2012)
- D. Cerebrovascular ischemic disease including ischemic or hemorrhagic stroke, vascular stenosis, transient ischemic accident (TIA), cerebrovascular occlusive disease documented on diagnostic neuroimaging, or symptoms that may reflect cerebrovascular disease (Easton et al, 2009)
- E. New onset or worsening of peripheral artery occlusive disease (eg, renal artery, mesenteric artery, femoral artery) or symptoms that may reflect peripheral vascular disease
- F. Retinal vascular thrombosis, both venous and arterial
- G. Venous thromboembolism where significant compromise of organ function or other significant consequences could result (eg, pulmonary embolism, portal vein thrombosis, renal vein thrombosis) or symptoms that may reflect venous thrombosis

ARIAD may request additional information to the study sponsor on observed AESIs and this information should be provided in a timely fashion (ie, within 2 business days of the study sponsor awareness).

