10.52 Death

Any death occurring within 30 days of the last dose, regardless of attribution to an agent/intervention under an IND/IDE requires expedited reporting within 24-hours.

Any death occurring greater than 30 days with an attribution of possible, probable, or definite to an agent/intervention under an IND/IDE requires expedited reporting within 24-hours.

Reportable categories of Death

- Death attributable to a CTCAE term.
- Death Neonatal: A disorder characterized by cessation of life during the first 28 days of life.
- Death NOS: A cessation of life that cannot be attributed to a CTCAE term associated with Grade 5.

- Sudden death NOS: A sudden (defined as instant or within one hour of the onset of symptoms) or an unobserved cessation of life that cannot be attributed to a CTCAE term associated with Grade 5.
- Death due to progressive disease should be reported as **Grade 5 “Neoplasms benign, malignant and unspecified (incl cysts and polyps) – Other (Progressive Disease)”** under the system organ class (SOC) of the same name. Evidence that the death was a manifestation of underlying disease (e.g., radiological changes suggesting tumor growth or progression: clinical deterioration associated with a disease process) should be submitted.

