13.0 Treatment/Follow-up Decision at Evaluation of Patient

- 13.1 Patients who are CR, PR, or SD will continue treatment per protocol.
- 13.2 Patients who develop PD while receiving therapy will go to the event monitoring phase.
- 13.3 Patients who go off protocol treatment for reasons other than PD will go to the event monitoring phase per Section 18.0.
- 13.4 A patient is deemed *ineligible* if after registration, it is determined that at the time of registration, the patient did not satisfy each and every eligibility criteria for study entry. The patient may continue treatment off-protocol at the discretion of the physician as long as there are no safety concerns, and the patient was properly registered. The patient will go directly to the event monitoring phase of the study (or off study, if applicable).
- If the patient received treatment, all data up until the point of confirmation of ineligibility must be submitted. Event monitoring will be required per Section 18.0 of the protocol.

- If the patient never received treatment, on-study material and the End of Active Treatment/Cancel Notification Form must be submitted. No further data submission is necessary.
- 13.5 A patient is deemed a *major violation*, if protocol requirements regarding treatment in cycle 1 of the initial therapy are severely violated that evaluability for primary end point is questionable. All data up until the point of confirmation of a major violation must be submitted. The patient will go directly to the event-monitoring phase of the study. The patient may continue treatment off-protocol at the discretion of the physician as long as there are no safety concerns, and the patient was properly registered. Event monitoring will be required per Section 18.0 of the protocol.
- 13.7 A patient is deemed a *cancel* if he/she is removed from the study for any reason before any study treatment is given. On-study material and the End of Active Treatment/Cancel Notification Form must be submitted. No further data submission is necessary.

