16.32 Definitions and Analyses of Secondary Endpoints

- 16.321 Progression-free survival time is defined as the time from registration to the earliest date of documentation of disease progression. If a patient dies without a documentation of disease progression the patient will be considered to have had disease progression at the time of their death. In the case of a patient starting treatment and then never returning for any evaluations, the patient will be censored for progression 1 day post-registration. The distribution of progression-free survival time will be estimated using the method of Kaplan-Meier (1958).
- 16.322 Survival time is defined as the time from registration to death due to any cause. The distribution of survival time will be estimated using the method of Kaplan-Meier (1958).
- 16.323 CA 19-9 response is defined to be a $\geq 50\%$ reduction from baseline. The CA 19-9 response rate will be estimated by the number of CA 19-9 responses divided by the total number of evaluable patients. A confidence interval will be calculated based on the binomial distribution.
- 16.324 Adverse Events: All eligible patients that have initiated treatment will be considered evaluable for assessing adverse event rate(s). The maximum grade for each type of adverse event will be recorded for each patient, and frequency tables will be reviewed to determine patterns. Additionally, the relationship of the adverse event(s) to the study treatment will be taken into consideration.

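### Adverse event assessment is not scheduled at End of treatment or in the 30 days after the last dose, so non-serious Grade 2 to 4 events in that period depend on unscheduled reporting

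*Combined protocol and SAP*

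**What the plan says.** **Schedule.** Section 4.0 marks the row "Adverse event assessment" at screening, on Cycle 1 Days 8, 15 and 22, and on Day 1 of Cycle 2 and beyond. The End of treatment cell is empty. In the same column the row "History and exam, wt, ECOG" is marked, as are vitals, hematology and chemistry. End of treatment is the last column.

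**Forms and follow-up.** Section 18.1 ties the adverse event form to evaluations during treatment. The follow-up table lists only the Event Monitoring form: every 6 months, at progression, at death and at a new primary. Section 13.2 sends patients who progress to that phase, and Section 13.3 covers the rest: "Patients who go off protocol treatment for reasons other than PD will go to the event monitoring phase per Section 18.0".

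**Reporting rules outside the schedule.**
- Section 10.4 sets expedited reporting for serious events "within 30 Days of the Last Administration of the Investigational Agent/Intervention", and later if at least possibly related.
- Section 10.52 covers "Any death occurring within 30 days of the last dose, regardless of attribution".
- On vascular events, Section 10.41 says "All AESIs, whether SAEs or not, must be reported within 2 business days" of sponsor awareness.
- Section 10.6 asks for listed events to be graded at every evaluation. Sections 10.611 and 10.612 add other related Grade 2 events and all other Grade 3-4 events, with no end date.
- Section 10.62 refers late events to a forms packet that is not part of the documents.
- Section 10.14 uses another clock: serious events "until 4 weeks after the patient has stopped study participation must be reported".

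**Analysis.** Section 16.324 states: "The maximum grade for each type of adverse event will be recorded for each patient". This serves secondary goal 2.22, the adverse event profile.

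**The concern.** The plan requires certain non-serious events to be submitted but schedules no occasion to look for them once the last Day 1 visit has passed. The End of treatment visit takes place, with an exam and laboratory tests, yet its adverse event cell is blank. A site that works from the grid may not complete an adverse event form there. A site that works from Section 10.6 would.

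After that visit nothing is scheduled until event monitoring, which may be 6 months away. A maximum over fewer assessments cannot exceed a maximum over more, so any loss pushes the maximum-grade tables in one direction, downward. With at most 30 patients accrued, a few missed Grade 3 events would visibly change the reported profile.

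**Working it through.** The plan states no figure for this point. Two checks are possible: which events lack scheduled ascertainment, and how much calendar time is involved.

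**1. Coverage after the last scheduled assessment**

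| Event type | Covered after stopping? | Source |
|---|---|---|
| Serious, within 30 days of last dose | Yes, event-driven | 10.4 |
| Serious and related, after 30 days | Yes, event-driven | 10.4, footnote 1 |
| Death within 30 days | Yes, event-driven | 10.52, 10.6131 |
| Vascular event of special interest, serious or not | Yes, event-driven | 10.41 |
| Non-serious related Grade 2 | Submission required, no scheduled assessment | 10.611, 4.0, 18.1 |
| Non-serious Grade 3-4 | Submission required, no scheduled assessment | 10.612, 4.0, 18.1 |

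Only the last two rows are open. The separate notification form for other Grade 4-5 events in Section 10.4 applies during treatment only.

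**2. Share of calendar time**

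Inputs: 28-day cycles and the adverse event row (Section 4.0), and a 30-day window after the last dose (Sections 9.3, 10.4 and 10.6131). Applying that window to non-serious events is my assumption, because the plan gives routine collection no end date. With stop day S and last scheduled assessment day A:

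share = (S + 30 − A) / (S + 30)

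- Stop at the week-8 scan: S = 57. Two cycles are 56 days, so Day 57 is Cycle 3 Day 1, where the assessment is marked, and A = 57. Share = 30/87 = 34%.
- Stop on Cycle 2 Day 14: S = 28 + 14 = 42, A = 29. Share = (72 − 29)/72 = 43/72 = 60%.
- Stop on Cycle 5 Day 14: S = 112 + 14 = 126, A = 113. Share = (156 − 113)/156 = 43/156 = 28%.

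If events are also graded at End of treatment, taken as the stop day, then A = S. The second and third cases become 30/72 = 42% and 30/156 = 19%. The first is unchanged. A check 30 days after the last dose would close the remainder.

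These are shares of time, not of events lost. The documents give no capture rate.

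**3. Accrual-suspension rule (Section 16.42), illustration only**

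The rule needs 4 or more of the first 20 treated patients with a related non-hematologic event of Grade 4 or higher. If the true rate is p and a fraction c is captured, the chance of reaching it is P(X ≥ 4) with X ~ Binomial(20, p × c). Both p and c are assumptions.

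| p | c = 1 | c = 0.9 | c = 0.8 | c = 0.7 |
|---|---|---|---|---|
| 0.20 | 0.589 | 0.497 | 0.401 | 0.304 |
| 0.30 | 0.893 | 0.830 | 0.743 | 0.631 |

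Most events that count here would also be serious and so reported under Section 10.4. The realistic value of c is therefore probably close to 1.

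**The case against.** The strongest reply is that the blank cell is an inconsistency rather than an absence of collection. End of treatment belongs to the Active Monitoring Phase, Section 10.6 applies to every evaluation, and the Section 18.1 column that holds the adverse event form also holds the End of Active Treatment form. A careful site would grade events there. This stands as a possible reading, but the grid points the other way and the text should settle it.

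Four stronger readings are tempting, and the documents do not support them.

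- *Events around stopping are systematically under-collected.* The 30-day windows govern expedited events and deaths, which do not wait for a visit. Section 10.62 sends late events to a forms packet whose content is unknown. What remains is a possible bias of unknown size.
- *The events that cause stopping are the ones missed.* Table 8.2 bases omission and discontinuation mostly on CTCAE grade, so such an event has generally been identified and graded when it occurs, and Sections 10.611 and 10.612 then require most of them to be submitted. Nor is follow-up wholly absent: Section 8.2 requires at least weekly follow-up for other non-hematologic events of Grade 3 or higher, although this does not cover every permanent discontinuation.
- *Two thirds of the risk window is uncovered for a stop at week 8.* Counting from Day 29 gives 58/87 = 67%, but this passes over the Cycle 3 Day 1 assessment due on Day 57. Section 7.2 also requires an evaluation at least every 28 days.
- *The suspension rule is weakened.* As shown above, this needs a capture loss that the reporting rules make unlikely.

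**Conclusion.** The point holds in a limited form. Sections 4.0 and 18.1 schedule no ascertainment of non-serious related Grade 2 or non-serious Grade 3-4 events after the last marked assessment, and the End of treatment cell is at odds with Section 10.6. Any resulting bias in the Section 16.324 tables is downward, and its size cannot be calculated from the documents.

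The time shares of 34%, 60% and 28% rest on a risk window from first dose to 30 days after the last dose. The 34% also assumes that the Day 57 visit is handled as Cycle 3 Day 1. If a site recorded it only as End of treatment, the blank cell would matter there too, which is a further reason to fill it.

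The two clocks for serious events are a secondary wording matter. If participation ends with the last dose, Section 10.14 stops at 28 days against 30, a difference of two days. If participation includes event monitoring, which runs up to 2 years after registration, Section 10.14 runs much longer. Neither reading shows under-collection.

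**What to change.** 1. In Section 4.0, mark adverse event assessment at End of treatment. In Section 18.1, require the adverse event form at that visit. The visit already includes an exam and laboratory tests, so the cost is wording and one form.
2. Preferably, add one adverse event check by telephone or chart review 30 days after the last dose, with the form in Section 18.1. This matches the window already used in Sections 9.3, 10.4 and 10.6131. The cost is one short contact and one form per patient, at most 30 in all.
3. State when routine collection of non-serious events ends, so that the tables in Section 16.324 refer to a defined period.
4. Reconcile the end of serious event reporting in Section 10.14 with Section 10.4, and name the event from which the days are counted.
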